Visit 11 must occur at least 10 weeks from final dose but no more than 12 weeks.

The Investigator and/or qualified study-site personnel will contact patients by phone at Week 2, Week 16, and Week 26 to discuss study compliance, address any questions related to study medication, and review adverse events.

- Protocol BCB114 consists of a 24-week controlled assessment period and a 28-week open-label extension period.
- The study includes 11 visits to the clinical study site. The study will begin with Visit 1 (Screening) to obtain written informed consent and assent, and assess patient eligibility. Patients will also be asked to participate in a lifestyle intervention program encompassing diet and physical activity modifications. Patient eligibility must be confirmed prior to randomization. The drug screen will be done locally. Eligible patients will return to the study site within 35 days following screening procedures for

randomization at Visit 2 (Week 0), the start of the controlled assessment period. At Visit 2 (Week 0), following baseline efficacy, safety, pharmacodynamic (PD), and pharmacokinetic (PK) assessments will be done. A medically-qualified staff member will demonstrate the preparation of SC study medication for the patient or a designated caregiver and will administer the first dose of SC study medication. In addition to receiving study medications, all patients will be asked to continue the lifestyle intervention program encompassing diet and physical activity modifications.

- At Week 2 and Week 16 of the controlled assessment period, patients will be contacted by phone by qualified study-site personnel to discuss study compliance, address any questions related to study medication, and review AEs.
- During the controlled assessment period, patients will return to the clinical study site at 4- and 6-week intervals at Visit 3 (Week 4), Visit 4 (Week 8), Visit 5 (Week 12), Visit 6 (Week 18), and Visit 7 (Week 24) to complete efficacy, PD, PK, and safety assessments.

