3.6.5.2 Safety and concomitant medications

Adverse events, hypoglycemic events and concomitant medications on the date of first dose of open-label EQW (Week 24 visit) will be assigned to the extension period as this is considered a conservative approach. Other safety assessments at the Week 24 visit will be considered to have been carried out pre-dose and will therefore be assigned to the controlled assessment period. This is reflected in the definitions below.

Controlled assessment period:

- For patients who do not enter the extension period, the controlled assessment period will be defined as date of first dose of randomized study medication to date of last dose of randomized study medication + 7 days (or + 90 days after last dose of study medication for reporting of serious adverse events (SAEs) and other clinically significant or related AEs).
- For patients who go on to enter the extension period, the controlled assessment period for all safety parameters except AEs, hypoglycemic events and concomitant medications will be defined as date of first dose of randomized study medication to date of first dose of open-label EQW. For AEs, hypoglycemic events and concomitant medications, the controlled assessment period will be defined as date of first dose of randomized study medication to date of the first dose of open-label EQW – 1 day, in order for AEs, hypoglycemic events and medications recorded on the date of first dose of open-label EQW to be assigned to the extension period.

Extension period: For all safety parameters, except AEs, hypoglycemic events and concomitant medications, the extension period will be defined as date of first dose of open-

label EQW + 1 to date of last dose of open-label EQW + 7 days. For AEs, hypoglycemic events and concomitant medications, the extension period will be defined as date of first dose of open-label EQW to date of last dose of open-label EQW + 7 days (or + 90 days for SAEs and other clinically significant or related AEs). The extension period will only be defined for patients who enter the extension period and receive at least one dose of open-label EQW.

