4.2.4.1 Adverse event analysis

Adverse events (AE) will be classified in accordance to the Medical Dictionary for Regulatory Activities (MedDRA) dictionary. All adverse events will be coded using the latest available version of MedDRA by the database lock.

Treatment-emergent AEs (TEAE) are defined as AEs occurring after the first dose of study medication through the end of the treatment plus 7 days (or + 90 days for SAEs and other clinically significant or related AEs), including AEs collected after patients initiate glycemic rescue therapy.

AEs occurring after Study Termination but considered by the Investigator as clinically significant and as related to study medication or study procedure, and SAEs occurring within 90 days of the last administration of study medication or EQW if in the extension phase will be recorded on the AE eCRF and reported in the AE listing.

Any AE that is recorded as the reason for study discontinuation will be considered an adverse event leading to discontinuation (DAE) regardless of the date recorded. All DAEs will be reported regardless of when they occurred. Note, any AE that is a DAE under these rules will also count as an AE when reporting.

Off-treatment AEs will be defined for the following:

- Treatment completers to Week 52: An AE that occurs between Week 52 to Week 62 and starts the day after last dose of open-label EQW + 7 days (or + 90 days for SAEs and other clinically significant or related AEs). Only patients completing study medication to Week 52 will be considered. Patients completing study medication to Week 52 but who withdraw prior to Week 62 will also be included.
- Premature discontinuation: An AE that starts the day after last dose of study medication + 7 days (or + 90 days for SAEs and other clinically significant or related AEs), for patients who discontinue study medication before Week 24 or Week 52.

AEs for the combined periods are those that occur during the Treatment period or post-treatment.

AEs with a start date prior to the first administration of study medication will be classified as pre-treatment (non-treatment emergent).

AEs with a stop date prior to the date of the first administration of study medication will be classified as pre-treatment (non-treatment emergent) AEs.

In case of missing AE severity, AE causality, or AE seriousness, a worst-case approach will be used. For AE missing severity, the AE will be considered severe; for missing causality, the

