AE will be considered as possibly-related to study medication; for missing seriousness, the AE will be considered serious.

On-treatment AEs (TEAEs) will be summarized for 24-week controlled assessment period and 28-week extension period as defined below. Off-treatment AEs for treatment completers to Week 52 will be tabulated where required. Off-treatment AEs for patients who prematurely discontinued will be listed only.

An overall summary of number and percentage of patients experiencing at least 1 TEAE will be presented for EQW and PBO. The summary will be presented by study period (controlled assessment period and extension period). A summary of AEs during the Treatment period for patients with actual treatment EQW during the controlled assessment period will be provided. The AE summary will include the number and percentage of patients experiencing any AE, any SAE, any AE related to treatment per Investigator's discretion, any AE leading to treatment discontinuation, any AE leading to study withdrawal, and any fatal AE.

Additionally, all TEAEs will be summarized for each treatment group as follows:

- AEs summarized by SOC, PT, maximum intensity (Mild, Moderate, Severe), causality (Not related, Related), action taken, and outcome.
- SAEs summarized by SOC and PT, maximum intensity (Mild, Moderate, and severe), causality (Not related, Related).
- AEs leading to treatment discontinuation summarized by SOC and PT.
- Frequent AEs (AE with at least 5% incidence in any treatment) summarized by preferred term.
- Non-serious frequent AEs summarized by SOC and PT.
- Potentially immune-related AEs summarized by antibody status (positive versus negative), SOC and PT.
- Potentially immune-related AEs summarized by antibody titer (higher: ≥ 625 versus low: < 625), SOC and PT.
- Potentially immune-related injection site-related AEs summarized by SOC and PT.

Summaries by maximum intensity will be presented separately for the controlled assessment period (Safety analysis set) and extension period (subset of Safety patients who received open-label EQW during the extension period). All other AE summary tables will be presented by study period in a single table.

Potentially immune-related AEs will be identified using the PTs given in [Appendix B4](#).

Injection site-related AEs will be identified using AEs within higher-level term "Injection site reactions".

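### For on-schedule completers, SAEs and related AEs are counted over 24 weeks in the controlled column but 40 to 41 weeks in the extension column, and cannot enter the off-treatment category

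*SAP*

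**What the plan says.** SAP 4.2.4.1 names the two summary periods by length: "On-treatment AEs (TEAEs) will be summarized for 24-week controlled assessment period and 28-week extension period as defined below". Maximum-intensity summaries are shown separately by period. For the rest, "All other AE summary tables will be presented by study period in a single table". Denominators are numbers of patients: the Safety set for the controlled column, and the Safety patients who received open-label EQW for the extension column. No rate per unit of person-time is planned.

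SAP 3.6.5.2 sets the AE windows:

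- Controlled period, patients who go on to the extension: "date of first dose of randomized study medication to date of the first dose of open-label EQW – 1 day", with no tail.
- Controlled period, patients who do not: last randomized dose + 7 days, "or + 90 days after last dose of study medication for reporting of serious adverse events (SAEs) and other clinically significant or related AEs".
- Extension: from the first open-label dose to the "date of last dose of open-label EQW + 7 days (or + 90 days for SAEs and other clinically significant or related AEs").

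For patients who complete treatment to Week 52, SAP 4.2.4.1 defines an off-treatment AE by two conditions. It falls between Weeks 52 and 62, and it "starts the day after last dose of open-label EQW + 7 days (or + 90 days for SAEs" and other clinically significant or related AEs). Only this group's off-treatment AEs are tabulated, where required; those of early discontinuers are listed. Protocol 3.1 ties the last visit to the final dose: "Visit 11 must occur at least 10 weeks from final dose but no more than 12 weeks".

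**The concern.** A table with one column per period invites the reader to compare the columns. If one column accumulates events for much longer, its percentage is higher at an unchanged event rate. For patients switching from placebo, that could be taken for an effect of EQW. For patients on EQW throughout, it could be taken for risk rising with time on drug. The labels of 24 and 28 weeks hide the difference, because the 90-day tail applies only to some categories and, for patients who continue, only to the extension column.

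The same tail makes the rows of the extension column unequal. Related events are counted for longer than non-serious unrelated ones, which raises the apparent share of related events.

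The off-treatment definition takes the 90-day clause over as its starting point and adds a Week 62 limit. If that limit comes before the starting point, the category cannot hold the events that matter most in follow-up. Safety is one of the two primary objectives, so these tables carry weight.

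**Working it through.** Convention: Day 1 is the first randomized dose, and Week w is Day 7w + 1.

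**Inputs**
- First open-label dose: Week 24, Day 169 (SAP 1.2, note to Figure 1).
- Last open-label dose: Week 52, Day 365, as SAP 1.2 words it. The supply in Protocol 5.7 is 4 + 12 + 12 = 28 weekly doses from Week 24. Taken weekly, these end at Week 51, Day 358. Both are carried through.
- Visit 11: 70 to 84 days after the final dose (Protocol 3.1).

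**Stated lengths.** Controlled period: Day 1 to Day 168 = 168 days = 24.0 weeks. Nominal extension: Week 24 to Week 52 = 28 weeks. Both stated lengths reproduce.

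**Windows actually counted, patient completing both periods.** Extension days = last dose + tail − 169 + 1.

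| Column | Other AEs (+7) | SAEs, clinically significant or related AEs (+90) |
|---|---|---|
| Controlled | 168 days (24.0 wk) | 168 days (24.0 wk) |
| Extension, last dose Week 51 | 358 + 7 − 168 = 197 (28.1 wk) | 358 + 90 − 168 = 280 (40.0 wk) |
| Extension, last dose Week 52 | 365 + 7 − 168 = 204 (29.1 wk) | 365 + 90 − 168 = 287 (41.0 wk) |
| Ratio to controlled | 1.17 to 1.21 | 1.67 to 1.71 |

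The design alone accounts for a ratio of about 1.2. The tail adds 90 − 7 = 83 days to some rows only.

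SAP 4.2.4.1 also says that events after Study Termination go to the AE listing. If that means listing only, the extension window stops at Visit 11. With the last dose at Week 52 it is then 365 + 70 − 168 = 267 days (38.1 weeks) to 365 + 84 − 168 = 281 days (40.1 weeks), so the imbalance remains.

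**Patients who do not enter the extension.** Their controlled-column window for these categories is last dose + 90 days. It runs from 1 + 90 = 91 days (13 weeks, one dose) to 162 + 90 = 252 days (36 weeks, last dose Week 23). Windows therefore differ within that column too.

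**Illustration only.** The documents give no SAE or related-AE rate. Assume a constant rate and 168 against 280 days. Incidence p in the controlled column becomes 1 − (1 − p)^(280/168):
- 5% becomes 8.2%
- 10% becomes 16.1%
- 20% becomes 31.1%

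With + 7 days throughout (197 days), 10% would become 1 − 0.9^(197/168) = 11.6%.

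**Off-treatment category, Week 52 completers.** The earliest eligible start for a serious, clinically significant or related AE is last dose + 91.
- Last dose Week 51: Day 449. Week 62 is Day 435; latest Visit 11 is 358 + 84 = Day 442.
- Last dose Week 52: Day 456. Week 62 is Day 435; latest Visit 11 is 365 + 84 = Day 449.

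Eligible days: 0 in both cases. Other AEs are eligible from last dose + 8. That gives Day 366 to 435 = 70 days, or Day 373 to 435 = 63 days.

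**The case against.** The strongest reply is that nothing planned as an inference is harmed. The safety objective compares EQW with placebo over 24 weeks, the extension is uncontrolled, and the SAP plans no test of one period against the other. The 90-day SAE window comes from the protocol (6.4.4 and 12.6.7.1), and it suits a depot that Protocol 1.1 describes as releasing drug over days to months. No event is lost. Late SAEs appear in the extension column and the AE listing, and for patients on EQW throughout also in the Treatment-period summary. Off-treatment is the complement of treatment-emergent, so an empty cell means that the events were counted elsewhere.

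These facts stand, and they rule out two readings that a reader might infer.

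- *The randomized comparison is biased.* The controlled column applies the same rule to both arms. The tail of non-entrants could lengthen one arm's window if discontinuation differed by arm, but the documents give only an overall 10% drop-out assumption.
- *The off-treatment table must show zero serious and related events, and so suggests clean washout.* The SAP specifies no such rows. A completer is defined by a Week 52 assessment, not by a Week 52 dose. A last injection at Week 49 leaves 1 eligible day before nominal Week 62, and one at Week 48 leaves 8. None remain if Week 62 means Visit 11.

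The reply does not answer the layout. One table shows both periods under nominal lengths that are wrong for these categories, without person-time.

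**Conclusion.** The point holds for descriptive safety output and should be corrected. For patients completing both periods, SAEs and clinically significant or related AEs are counted 1.67 to 1.71 times as long in the extension column as in the controlled column, and 83 days longer than other AEs within the extension column. Crude percentages for these categories cannot be compared across columns. For schedule-adherent Week 52 completers, the off-treatment definition contains no eligible day for these events.

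This rests on weekly dosing to Week 51 or 52, a first open-label dose at Week 24, and Visit 11 inside its window. Patients who stop early have other windows. The percentages in the illustration should not be read as an expected distortion: the rate is assumed, and a constant hazard for related AEs after injections stop is doubtful. The 90-day window is not itself an error. The faults are its uneven use across columns and its place in the off-treatment definition. The efficacy analyses are untouched.

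**What to change.** Keep the protocol's 90-day SAE window for the overall Treatment-period summary and the listings. In the by-period tables:

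1. End the on-treatment columns at last dose + 7 days for all AE categories. For patients who continue, the controlled column still ends the day before the first open-label dose.
2. Show every collected AE starting from day 8 to day 90 after the last dose in one separately labelled follow-up column. Include related non-serious AEs recorded after Visit 11. Footnote that other AEs are collected only to Visit 11.
3. Give patient-years at risk and events per 100 patient-years for each column. This also covers the remaining ratio of 1.17 to 1.21.
4. Remove the 90-day clause from the completers' off-treatment definition. These events then have 63 to 70 eligible days up to Week 62.
5. Declare the change in SAP Section 5.

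The cost is wording in SAP 3.6.5.2 and 4.2.4.1, new period flags and a person-time derivation, with no new data collection. The extension column will show fewer SAEs and related AEs. For these tables the plan also departs from the protocol's on-treatment definition, although Protocol 12.6.7.1 leaves the detailed classification rules for the extension to the SAP.

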4.2.4.2 Injection-site reactions

Proportions of patients reporting different injection site reactions at Visit 3 (Week 4) through Visit 10 (Week 52).

Injection-site reactions will be identified from the AE dataset using the higher-level term (HLT) “Injection site reactions”. Injection-site reactions reported on the INJECT eCRF will not be included in summaries as this eCRF was introduced part-way through the study and therefore does not provide a complete picture of the number of injection-site reactions. Data reported on the INJECT form will be listed only.

The number and percentage of patients reporting different injection site reactions, per the AE dataset, will be summarized by visit (see Section 4.3.3 for details on visit windows for injection site reactions). This will be provided separately for both the Safety analysis set during the controlled assessment period and for the subset of Safety patients who received open-label EQW during the extension period for the Treatment period. The injection site reactions will be additionally repeated by injection device type i.e. pre-filled syringe or dual-chamber pen. All patients randomized to the study on or after 12th August 2018 are dispensed dual chamber pen devices.

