6.4.10 Injection site reaction assessment

Small, asymptomatic, SC nodule formation at the injection site is an expected event associated with sustained release delivery systems.

The assessment of injection site reactions will be performed by the Investigator or subinvestigator according to the schedules presented in the Study Plan (Table 1) and Section 6.2.

Assessments should be done by interviewing the patient and/or the patient's parent(s) or caregiver(s), and be performing physical assessment of the injection site. All relevant information regarding injection site reactions, including reaction type, location, severity, and action taken, should be reported by the Investigator in the Injection Site Reaction Module of the eCRF, including all injection site reactions that meet the criteria for an AE.

Classification of whether an injection site reaction is an AE or not an AE should be made based on the definition of an AE as described in Section 6.4.1. Determination of whether an injection site reaction AE should be classified as serious should be done based on the standard SAE definition as described in Section 6.4.2, as with all other AEs.

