12.2.2 Secondary endpoints

- Change in HbA1c from baseline Visit 2 (Week 0) to Visit 10 (Week 52), and to each intermediate visit as applicable
- Change in fasting plasma glucose concentration from baseline Visit 2 (Week 0) to Visit 7 (Week 24), Visit 10 (Week 52), and to each intermediate visit as applicable
- Proportions of patients achieving HbA1c goals of $\leq 6.5\%$ and $< 7.0\%$ at Visit 7 (Week 24), Visit 10 (Week 52), and at each intermediate visit
- Change in body weight from baseline Visit 2 (Week 0) to Visit 7 (Week 24), Visit 10 (Week 52), and to each intermediate visit as applicable
- Change in fasting insulin and C-peptide from baseline Visit 2 (Week 0) to Visit 7 (Week 24), Visit 10 (Week 52), and to each intermediate visit as applicable
- Change in beta-cell function (HOMA-B) and insulin sensitivity (HOMA-S) as measured by homeostasis model assessments in EQW patients not taking insulin from baseline Visit 2 (Week 0) to Visit 7 (Week 24), Visit 10 (Week 52), and to each intermediate visit as applicable
- Change in lipids from baseline Visit 2 (Week 0) to Visit 5 (Week 12), Visit 7 (Week 24), Visit 10 (Week 52), and to each intermediate visit as applicable
- Change in blood pressure from baseline Visit 2 (Week 0) to Visit 7 (Week 24), Visit 10 (Week 52), and to each intermediate visit as applicable
- Plasma exenatide concentrations at baseline Visit 2 (Week 0), Visit 7 (Week 24), Visit 10 (Week 52), and each intermediate visit, as applicable

- Proportions of patients discontinuing the study, needing rescue due to failure to maintain glycemic control, and number of rescue episodes at Visit 7 (Week 24), Visit 10 (Week 52), and at each intermediate visit
- Proportions of patients reporting different injection site reactions at Visit 3 (Week 4) through Visit 10 (Week 52).

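### SAP 4.2.4.2 counts only injection-site reactions coded as AEs, which is narrower than the protocol endpoint, and SAP Section 5 does not record the change

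*SAP*

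**What the plan says.** **The endpoint.** Protocol 12.2.2 lists as a secondary endpoint "Proportions of patients reporting different injection site reactions at Visit 3 (Week 4) through Visit 10 (Week 52"). It is not limited to AEs. SAP 3.4 carries the same endpoint, now among the safety variables.

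**How reactions are recorded.** Protocol 6.4.10 has the investigator question the patient or caregiver and examine the site. The findings go into the "Injection Site Reaction Module of the eCRF, including all injection site reactions that meet the criteria for an AE". The AE decision is a separate step: "Classification of whether an injection site reaction is an AE or not an AE should be made based on the definition of an AE". The same section warns that "Small, asymptomatic, SC nodule formation at the injection site is an expected event associated with sustained release delivery systems".

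**What is counted.** SAP 4.2.4.2 takes reactions from AE records under one MedDRA higher-level term. On the dedicated form it says "Injection-site reactions reported on the INJECT eCRF will not be included in summaries as this eCRF was introduced part-way through the study", and then "Data reported on the INJECT form will be listed only". It adds that "The injection site reactions will be additionally repeated by injection device type"; pens go to patients randomised on or after 12 August 2018.

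**What is declared.** SAP Section 5, which sets out departures from the protocol, mentions neither the AE-only source nor the move of this endpoint from secondary to safety.

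**The concern.** The protocol separates a reaction from a reaction that is an AE, and defines the endpoint on the first. The SAP keeps the endpoint's wording but tabulates the second. A reader of the study report would take the table to be the protocol endpoint.

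The excluded reactions are not a curiosity. The protocol expects small symptomless nodules with this type of product, and these are the findings an investigator might see on examination and reasonably judge not to be AEs. In a paediatric trial of a weekly injection, how often they occur is something the report should state.

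The SAP's reason, that the form started late and is incomplete, explains why INJECT cannot supply an all-patient count. It does not explain leaving INJECT out of every summary. Each source is incomplete in its own way: the AE dataset covers all patients but one class of reaction, and INJECT covers both classes but only some of the patients.

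**Working it through.** The plan gives no figure for this endpoint, so there is none to reproduce. The main check is textual.

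**1. Texts side by side**

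| Item | Protocol | SAP |
|---|---|---|
| Endpoint | Patients with injection-site reactions, by kind (12.2.2) | Same wording (3.4, 4.2.4.2) |
| Which reactions | AE and non-AE (6.4.10) | AE-coded only (4.2.4.2) |
| Source | Dedicated module, after interview and examination (6.4.10) | AE dataset, one higher-level term (4.2.4.2) |
| Module data | Where reactions are recorded | Listing only |
| Change declared | n/a | Not in Section 5 |

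I take the INJECT form of the SAP to be the protocol's module; the documents do not say so outright.

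**2. Direction.** AE-coded reactions are a subset of all reactions. A patient with at least one AE-coded reaction also has at least one reaction, but not the reverse. So the tabulated proportion is at most the endpoint proportion.

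**3. Size (illustration on assumed inputs).** Let p be the true proportion of patients with a reaction, and s the share of those patients who have at least one AE-coded reaction. Both are per patient, because the endpoint is a proportion of patients.

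Tabulated proportion = p × s. Patients missed = N × p × (1 − s), with N = 77 × 5/7 = 55 on exenatide.

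| p | s | Tabulated | Missed of 55 |
|---|---|---|---|
| 20% | 25% | 5% | 8.25 |
| 20% | 50% | 10% | 5.5 |
| 20% | 75% | 15% | 2.75 |
| 20% | 100% | 20% | 0 |
| 40% | 25% | 10% | 16.5 |
| 40% | 50% | 20% | 11 |
| 40% | 75% | 30% | 5.5 |
| 40% | 100% | 40% | 0 |

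For example, 0.20 × 0.25 = 0.05, and 55 × 0.20 × 0.75 = 8.25. The documents give neither p nor s.

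**4. Device table.** Both device groups are counted from the AE dataset. With equal true proportions, the apparent gap (pen minus syringe) = p × (s_pen − s_syringe). With p = 20%:

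- s = 50% in both groups: gap 0.
- 50% syringe, 25% pen: 0.20 × (0.25 − 0.50) = −5 points.
- 50% syringe, 75% pen: 0.20 × (0.75 − 0.50) = +5 points.

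Under-counting alone produces no false gap. One appears only if AE capture differed between the two enrolment periods, and it could go either way.

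**The case against.** **The SAP's choice is open and reasoned.** It says that INJECT is incomplete, uses the source collected throughout, states that the summary rests on the AE dataset, and still lists INJECT. This stands as a defence of the all-patient table's source. It does not cover the unchanged endpoint wording, the silence of Section 5 or the absence of any INJECT summary.

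**Many reactions may be AEs anyway.** The protocol's AE definition includes signs, and SAP Appendix B4 lists injection-site nodule, papule, induration and erythema among the AE terms it looks for. This also stands: s could be close to 100%, and the shortfall small.

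**Little hangs on it inferentially.** The endpoint is descriptive and lies outside the testing hierarchy in SAP 4.2.3.2. That is correct; neither the primary analysis nor the error rate is affected.

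**A stronger reading is tempting.** A reader might infer that the syringe-versus-pen comparison is confounded with the introduction of the INJECT form, or that AE-type reactions entered only on that form are lost. The documents do not establish either:

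- Both device groups draw on the same AE dataset, so two instruments are not being mixed.
- INJECT's start is not dated. The Amendment 03 summary of changes lists no injection-site endpoint and the December 2017 protocol does, which suggests the form came with that edition. If so, it preceded the pens, and some syringe patients had it as well.
- Protocol 6.4.10 does not say that the module replaces the AE page, and Protocol 6.4.3 requires AEs of enrolled patients to be entered in the eCRF. At most, the flow between forms is unclear.

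A large false device gap would also need nearly complete AE capture with the syringe and poor capture with the pen. Yet reactions judged not to be AEs go uncounted in both groups.

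**Conclusion.** The point holds as a mismatch between endpoint and table. SAP 4.2.4.2 reports injection-site reaction AEs under the name of a wider endpoint. Non-AE reactions are left out of every summary, and Section 5 does not say so. The direction is certain: the table equals or understates the endpoint. The size is unknown, and the figures above rest on assumed values of p and s.

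On devices, the documents show only that the split follows randomisation date, so the comparison is non-randomised, tied to enrolment period and descriptive. It may also be affected if AE reporting changed when INJECT was introduced, but nothing in the documents shows that it did.

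The change is worth making because it aligns the reported result with the stated endpoint at small cost. It does not threaten the trial's main conclusions.

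**What to change.** In the SAP:

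1. **4.2.4.2, all-patient table.** Keep the AE dataset as the source and title the table 'Injection-site reaction AEs'.
2. **4.2.4.2, new table.** Summarise INJECT reactions descriptively by type, visit and randomised arm over the controlled period, for patients first dosed after the form went live. State that date, and whether AE-type reactions on INJECT were also entered on the AE page. Because the subset is defined by date of first dose, the comparison between arms is not selected on what happened after treatment began.
3. **4.2.4.2, device table.** Label it as a non-randomised comparison tied to enrolment date, with a note that a change in AE reporting when INJECT began cannot be excluded.
4. **Section 5.** Record the restriction to AE-coded reactions and the move of the endpoint from secondary to safety.

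INJECT records should not be merged into the all-patient count. That would add a source available only later in the trial, and so create the mid-study change of instrument that the present table avoids. It would also need an AE flag on INJECT, which the documents do not describe.

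The cost is some wording and one descriptive table from data already collected. The drawback is that the INJECT table covers only part of a 77-patient trial, so it will be imprecise, and it may show a higher reaction rate than the AE table.
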